## **SECTION 5 STUDY ENROLLMENT AND WITHDRAWAL**

### **5.1 Study Population, Recruitment and Retention**

Potentially eligible participants will be identified through CNMC's medical records prior to routine clinic visits. The study will also be advertised to T1D patients in the CADP through a trained research assistant (RA) in clinic waiting rooms at the time of their routine clinic visits. If a participant expresses interest and meets eligibility criteria, a screening visit will be scheduled for directly before or after the patient's routinely scheduled clinic visit. Participants will also be recruited via word of mouth and social media, recruiting children with T1D and their parents willing to travel to Children's National for the in person components. During the screening visit the child and their parent/guardian (referred to as parent) will complete a LCSB screener questionnaire and brief eligibility checklist, including the Eating Attitude Test (EAT) administered by the RA to determine initial eligibility (which will be confirmed by [name]). Eligible participants and their parent will provide assent and consent, respectively.

To encourage adherence and retention, we will provide \$340 for study participation (this includes \$120 for the baseline visit, \$120 for the follow-up visit, \$30 for booster session, \$40 for 4 food records, \$30 for the screening visit). The subset of participants who undergo DXA or BodPod will receive an additional \$50 per visit, for a total of up to \$440 compensation for study participation. Additional compensation will be provided to cover the cost of parking (parking voucher) or transportation (equivalent up to \$10) to Children's for study visits. We will also encourage retention by maintaining regular contact with study participants through text message/email reminders and the 6-week telemedicine booster session.

### **5.2 Inclusion Criteria (RCT)**

- Child is between 5 to 14 years old
- Child consumes  $\geq$  12 oz. of a LCSB with sucralose (+/- ace-K) or aspartame+ace-K per day
- Child has had a diagnosis of T1D for at least one year
- Parent/guardian has reliable phone and internet access
- Parent/guardian and child both speak English

#### **Inclusion Criteria (COVID-19 interviews)**

- Parent of child with T1D between 5 to 14 years old
- Parent of child who has had a diagnosis of T1D for at least one year
- Parent/guardian has reliable phone and internet access
- Parent/guardian speaks English fluently
- Parent of child enrolled in the Childhood and Adolescent Diabetes Program (CADP) at Children's National

### **5.3 Exclusion Criteria (RCT)**

- Child consumes foods with low-calorie sweeteners (e.g., sugar-free ice cream, light yogurt, sugar-free oatmeal) more than 3 times per week
- Child consumes condiments with low-calorie sweeteners (e.g., sugar-free pancake syrup, sugar-free jam, reduced sugar ketchup) more than 3 times per week
- Child has a poorly managed chronic disease other than T1D, acute illness, current or prior eating disorder as assessed by the EAT or is taking medications other than insulin

#### **Exclusion Criteria (COVID-19 interviews)**

- Not applicable.

### **5.4 Inclusion of Children**

We will study children 5-14 years, rather than older adolescents, because children of this age are more often monitored by their parents than older children, enabling us to more effectively engage parents to maximize intervention adherence. Children 4 years

and younger will be excluded because LCSB consumption is relatively low in this age group.

### **5.5 Recruitment**

The study (both the RCT and the COVID-19 interviews) will be advertised to the clinic patient populations and their parents through on-site recruitment in clinic waiting rooms and through searching CNMC medical records prior to their routine clinic visits, as well as via social media, list servs, and word of mouth. Potentially eligible patients will be provided with study information by in-person, via email, postal mail or by phone (recruitment letter for RCT enclosed).

For the COVID-19 interviews, if a parent expresses interest and meets eligibility criteria, they will be scheduled for a Zoom Telehealth interview at a day/time convenient for them.

For the RCT, if a participant expresses interest and meets initial eligibility criteria (assessed in person or via phone), a screening visit will be scheduled immediately before or after the patient's upcoming clinic visit to ensure minimal disturbance to clinic flow. If the patient is already using CGM, the participant will have the option to complete this screening visit remotely via Zoom Telehealth rather than in person. Given the large volume of children served by the participating sites, we do not anticipate any problems recruiting and retaining a diverse sample of children. If the potential participant has questions that the research assistant (RA)/clinical study coordinator (CRC) cannot answer, the RA/CRC will immediately contact [name].

### **5.6 Retention**

We will maximize retention by maintaining regular contact with RCT participants through text message/email reminders throughout the study. This will help us to develop rapport with the subjects. In addition, we will provide a total of \$340 for participating in the study. The subset of participants who undergo DXA or BodPod will receive an additional \$50 per visit, \$440 total. Compensation will be provided using the Forte payment system (analogous to ClinCard) at GW. For parents who participate in the COVID-19 interviews, compensation of \$50 will be provided and will be provided as a gift card.

### **5.7 End of Participation Criteria and Procedures**

Participants are free to withdraw from participation in the study at any time upon request. An investigator may terminate study participation if:

- The participant meets an exclusion criterion (either newly developed or not previously recognized) that precludes further study participation.
- The participant is unwilling or unable to comply with the study procedures.

This study may be temporarily suspended or prematurely terminated if there is sufficient reasonable cause. Written notification documenting the reason for study suspension or termination will be provided by the suspending or terminating party to participants, site investigators, the funding agency and regulatory authorities (e.g., OHRP). If the study is

prematurely terminated or suspended, the PI will promptly inform the IRB and will provide the reason(s) for the termination or suspension.

Circumstances that may warrant study termination or suspension include, but are not limited to:

- Determination of unexpected, significant, or unacceptable risk to participants
- Insufficient study team or site participant compliance to protocol requirements
- Data that are not sufficiently complete and/or evaluable
- Determination of futility

The study may resume once any concerns about safety, protocol compliance, data quality or funding are addressed and satisfy the sponsor, IRB and OHRP.

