## **SECTION 7 STATISTICAL CONSIDERATIONS AND ANALYSIS**

Our primary outcome is the difference in change in glycemic variability in those randomized to LCSB restriction compared to controls, calculated as difference in average daily TIR in Weeks 11 and 12 compared to Weeks -1 and 0. Because no prior study has assessed glycemic variability before and after LCSB restriction, we have powered our study using changes before and after LCS consumption. Suez et al., reported a  $1564 \pm 1852$  (mg·dL·120 mins) $^{-1}$  increase in glucose AUC post-LCS versus baseline, in 7 volunteers consuming saccharin (equivalent to 4-5 diet sodas per day) for 1 week. Using a similar effect size, 13 subjects per group will provide 80% power to detect differences in glycemic control before and after LCS restriction versus control (G\*Power; V3). Because 60% (4 of 7) of participants were considered LCS-responders by Suez, we will randomize 20 participants to the intervention and control, respectively (n=40). 48 subjects (24 per group) will account for 20% attrition. However, because prior studies conducted by Drs. [name] and [name] in this patient population have generated 70-80% usable CGM data, we will conservatively enroll 60 subjects (n=30 per group). We will use 1:1 block randomization stratified by LCSB type (sucralose or aspartame + ace-K) to lay the groundwork for evaluating potential differences in effects of sucralose versus aspartame in future studies.

Univariate analyses will be performed using an intention to treat approach. The maximum number of days of glycemic data will be used without imputations for missingness. Bivariate associations will be examined using cross tabulations, odds ratios, and chi-squared tests; boxplots, mean differences, and ANOVA, and correlations, as appropriate. We will identify and validate outliers and non-parametric tests will be used in the case of non-normal data. By establishing strengths of crude associations and highlighting irregular data, descriptive analyses will be a reference for more complex models. Changes in glycemic variability and other metabolic outcomes pre/post intervention will be compared between the groups using ANOVA. Hypothesis

testing will be two-sided with a type I error of 0.05. Analyses will be summarized using regression estimates, p-values, and 95% CI and performed using SAS 9.4.

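### Section 5.7 allows removal after randomisation with no further outcome collection, so the intention-to-treat comparison claimed in Section 7 is in practice an available-case analysis

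*Combined protocol and SAP*

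**What the plan says.** **Ending participation (Section 5.7).** Families may leave when they wish: "Participants are free to withdraw from participation in the study at any time upon request". Separately, "An investigator may terminate study participation if" one of two grounds applies: "The participant meets an exclusion criterion (either newly developed or not previously recognized) that precludes further study participation", or "The participant is unwilling or unable to comply with the study procedures". The section does not say whether outcomes are still collected afterwards, or how such a child is analysed.

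**Exclusion criteria (Section 5.3).** Several can arise during 12 weeks. One is "Child consumes foods with low-calorie sweeteners (e.g., sugar-free ice cream, light yogurt, sugar-free oatmeal) more than 3 times per week". A parallel criterion covers condiments, and others cover acute illness and any medication other than insulin.

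**Analysis (Section 7).** The analysis principle is stated as follows: "Univariate analyses will be performed using an intention to treat approach". On missing CGM data, the rule is: "The maximum number of days of glycemic data will be used without imputations for missingness". The primary outcome is the between-group difference in change, "calculated as difference in average daily TIR in Weeks 11 and 12 compared to Weeks -1 and 0", compared by ANOVA. The section defines no analysis set. It gives no rule for a child who lacks the whole Weeks 11-12 window, and no sensitivity analysis. Expected losses are met by enrolling more children.

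**Follow-up (Sections 4, 6.3 and 6.4).** Intervention children with differing degrees of adherence are to be interviewed at the Week 12 visit.

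**The concern.** Intention to treat needs outcomes from randomised children whether or not they followed their assignment. Section 5.7 allows a child to be taken out of the study for behaviour that occurs after randomisation, and the assignment may influence that behaviour. The primary endpoint cannot be computed for a child who leaves before Week 11, and HbA1c, the other primary outcome in Section 3.3, is drawn at the same follow-up visit. If those who leave differ from those who stay, and leaving differs by arm, the comparison of TIR change no longer has the protection of randomisation.

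There is a second consequence. Section 7 uses attrition rates to judge acceptability. Unless investigator removals are recorded apart from family withdrawals, that measure may mix staff decisions with families' own choices.

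**Working it through.** **1. What happens to a removed child.** Suppose participation ends in Week 8. CGM for Weeks -1 and 0 exists; CGM for Weeks 11-12 does not. Change = (mean daily TIR, Weeks 11-12) minus (mean daily TIR, Weeks -1 and 0), which is missing. An ANOVA on change omits the child. The rule on using all available days helps a child with some Weeks 11-12 data, but not one with none.

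**2. Can removal depend on arm?**
- Avoiding low-calorie sweetened beverages (LCSBs) is asked of the intervention arm; controls are asked to continue usual intake (Section 4). The two tasks differ, so the chance of non-compliance can differ.
- Daily beverage logs, food records and urine samples show staff who is adhering. The PI and dietitian run the orientation, and counselling differs by arm, so the discretion can be used by people who know the assignment.
- Intake of sweetened foods can change after randomisation. Removing LCSBs might raise it; the brochure for intervention families, which lists foods to avoid, might lower it. The documents do not settle which.

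**3. Loss implied by the plan's own rates.** Inputs from Section 7: 20% attrition, 70-80% usable CGM, 30 enrolled per arm. The plan's last two inflation steps reproduce: 20 x 1.2 = 24, and 24 / 0.8 = 30 per arm.

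| Assumption | Analysed per arm | Without primary outcome |
|---|---|---|
| Attrition and unusable CGM independent | 30 x 0.8 x 0.8 = 19.2; 30 x 0.8 x 0.7 = 16.8 | 1 - 0.64 = 36%; 1 - 0.56 = 44% |
| Full overlap | 30 x 0.8 = 24; 30 x 0.7 = 21 | 20%; 30% |

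The range is 20-44%, from all causes. The documents do not say how much would come from Section 5.7.

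**4. Illustration of bias (assumed inputs, not in the documents).** Let a share p of one arm be lost, and let its mean change differ by g SD from that of the children who stay. The arm mean among those analysed is then off by p x g. With p = 0.2 and g = 0.5 to 1.0, the bias is 0.2 x 0.5 = 0.10 SD to 0.2 x 1.0 = 0.20 SD.

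With no true effect, the two-sample t statistic then has noncentrality b / sqrt(1/n1 + 1/n2), where b is the bias in SD. The chance of a two-sided p below 0.05 is:

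| Analysed (n1 v n2) | b = 0.10 SD | b = 0.20 SD |
|---|---|---|
| 17 v 17 | 5.9% | 8.7% |
| 19 v 19 | 6.0% | 9.2% |
| 24 v 24 | 6.3% | 10.4% |
| 24 v 30 | 6.5% | 11.1% |

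The first two rows match the plan's rates under independence. The last row assumes that the one-sided loss is the only loss. The same figures apply whichever arm loses children and whatever the sign of g.

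**The case against.** The strongest reply is that Section 5.7 is a permissive clause that may rarely be used. Termination is discretionary. The non-compliance ground concerns study procedures, many of which (sensors, logs, visits) fall on both arms. The exclusion ground is limited to criteria that preclude further participation, and no re-screening is scheduled after randomisation. The Week 12 interviews presuppose that poorly adherent children are still present. All of this stands, and it rules out reading the protocol as removing every non-adherent child. It does not close the gap: the interview plan wants these children at Week 12, Section 5.7 lets them be removed before then, and no text says which prevails.

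The reply can also point out that Section 7 does have a missing-data rule and that enrolment is inflated for loss. Both are true. A reader might infer that missing data are not handled at all, or that this is a completer analysis. Neither is right: children with partial CGM are kept, so the analysis is available-case. But the rule works at the level of days, and a larger sample restores precision without removing bias.

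Finally, this is a pilot seeking preliminary evidence. That limits what hangs on the result, but Section 7 still plans two-sided tests at 0.05, and Section 2.2 hypothesises benefit.

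**Conclusion.** The conflict is real. As written, Sections 5.7 and 7 together produce an available-case comparison under an intention-to-treat label, and removal can be related to the arm. The size of any bias cannot be derived from the documents. The figures of 0.10-0.20 SD, and an error of about 6% to 9-11% depending on the number analysed, rest on assumed one-sided loss of 20% and an assumed gap of 0.5-1.0 SD.

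Three stronger readings are tempting but unsupported:
- **That the bias favours restriction.** This needs one-sided loss of intervention children with worse outcomes. Nothing in the documents establishes that pattern, and bias could run either way.
- **That Section 5.7 costs 36-44% of the sample.** That figure covers every cause, including sensor problems and voluntary withdrawal, and assumes independence; with full overlap it is 20-30%.
- **That the bias can be read as a fraction of the planning effect.** That effect is a before-and-after glucose AUC change in 7 volunteers taking saccharin, which is not on the scale of a between-arm TIR difference.

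**What to change.** **Section 5.7.** State that non-adherence to the assigned beverage, or a newly met exclusion criterion, does not by itself end outcome collection. Week 6 urine, Weeks 11-12 CGM and the follow-up visit are still sought unless consent or assent is withdrawn. Reconcile this with the Week 12 interview plan. The change concerns data collection only. Record investigator removals separately from family withdrawals in the attrition measure.

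**Section 7.** Define the primary analysis set as all randomised children, in the group assigned. Replace the ANOVA on change with a longitudinal model of TIR in both windows:
- Include child and child-by-period random effects. With a child effect alone, days within a window are treated almost as independent replicates of the change, and the standard error can be too small. Window means weighted by number of days are a simpler alternative.
- Include the randomisation stratum (LCSB type).
- Use baseline as an outcome or as a covariate, not both. As an outcome, it keeps children who have only one window.

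The model assumes that data are missing at random, which is doubtful if removal follows from adherence. Add one prespecified sensitivity analysis that shifts the missing outcomes over a stated range.

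**Cost.** Wording changes, a little more analysis, and some extra contact with families who have stopped following their assignment. No added visits or larger sample are needed, and Weeks 11-12 CGM is already worn at home.

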## **SECTION 6 STUDY PROCEDURES**

### **6.1 Informed Consent/Accent**

Informed consent is a process that is initiated prior to the individual's agreeing to participate in the study. It continues throughout the individual's study participation. Consent and assent forms will be IRB-approved. The parent and participant will be asked to read and review the consent and assent document(s), respectively. Extensive discussion of risks and possible benefits of participation will be provided to the participants and their families. The investigator will explain the research study to the participant and answer any questions that may arise. All participants will receive a verbal lay explanation of the purposes, procedures, and potential risks of the study and of their rights as research participants. Participants and their parent/guardian will have the opportunity to carefully review the consent and assent form and to ask questions prior to signing. Documentation of parent informed consent (written or using RedCap e-consent platform) and child assent is required for all participants prior to enrolling in the study of undergoing any procedures.

The parent and their child will sign the informed consent and assent, respectively, prior to beginning any study procedures. The participants may withdraw consent/assent at any time throughout the course of the study. A copy of the informed consent document(s) will be given to the participant/LAR for their records. The rights and welfare of the participants will be protected by emphasizing that the quality of their medical care will not be adversely affected if they decline to participate in this study.

If the participant has questions that the research assistant (RA)/clinical study coordinator (CRC) cannot answer, the RA/CRC will immediately contact [name] to provide clarification. The above described process for obtaining informed consent will also apply for obtaining consent from parents participating in the separate, qualitative interview about impacts of the COVID-19 pandemic on T1D management. No assent is needed for the qualitative interviews pertaining to impacts of the COVID-19 pandemic on T1D management because only the parent will participate.

## **6.2 Screening Process**

Subjects will be screened in-person or via Zoom Telehealth or phone before or after patient's upcoming clinic visit. Participants will be asked about each of the inclusion/exclusion criteria using the eligibility screener questionnaire, and the EAT, and will be asked to answer a brief prompt ("The COVID-19 pandemic has impacted management of my/my child's type 1 diabetes by....") about the impact of the COVID-19 pandemic on diabetes management. Any eligible participant will be invited to participate until our total sample size is reached.

## **6.3 Study Interventions and Follow-Up**

At the end of Week 12, participants and their parent will return for follow-up in the CRU. Participants will have their *DEXCOM G6™ sensor removed* and CGM data downloaded using DEXCOM Clarity™ software. Height and weight will be measured and another urine sample and blood draw performed. Those who had a DXA scan or BodPod at the baseline visit (n=30) will undergo a second DXA scan or BodPod, after which these participants and their parent will receive a consultation on the results. Those randomized to the intervention will be purposefully sampled and asked to complete a ~20-minute qualitative interview and ~5 minute satisfaction survey, together with their parent, about their study experience and the challenges of LCSB restriction. This will allow us to collect information from individuals with a range of perspectives and varying degrees of intervention adherence. Sampling will continue until saturation of ideas is reached or until all subjects in the intervention group are invited to be interviewed. There is no follow-up for participants in the COVID-19 interviews.

## **6.4 Description of Study Procedures/Evaluations**

We propose a two-arm randomized controlled trial (RCT) during which 60 children with T1D will either replace usual LCSB consumption with unsweetened still or seltzer water (LCSB restriction) or continue usual LCSB use (control) for 12 weeks. This will provide ample time to evaluate intervention feasibility and acceptability, while enabling us to generate preliminary evidence of whether LCSB restriction may improve cardiometabolic health.

Eligible participants will be scheduled for a baseline visit in the Clinical Research Unit (CRU) at CNMC. During the week prior, they will be instructed to continue usual dietary habits and complete an online photo-assisted 7-day food record, with parental assistance. While we recognize that parents are unlikely to accurately report all of their child's intake because they are not always with them (e.g., during school), dietary data for children under 14 years are most accurately reported when provided by the parent or child and parent combined.

The baseline visit will take place in the CRU, where height and weight will be measured, a spot urine sample will be collected, and a blood draw will be performed. Participants will have the DEXCOM G6™ sensor removed and their CGM data downloaded. In a subset of participants (n=30) a DXA scan or BodPod will also be performed, as R21 budget constraints preclude DXA or BodPod on all 60 subjects. Subjects will be

randomized (**Section C.6**) to 1) LCSB restriction or 2) usual LCSB intake (control). All participants (both control and LCSB restriction) and their parent will undergo a brief, 20-minute orientation where the PI and study dietitian will provide an introduction to the study, instructions on completing food records, *additional education on CGM and placement of the DEXCOM G6™ sensor*, and counseling on healthy eating strategies. *Parents will also receive 3 additional sensors (replacement in Week 1, placement in Week 11, and replacement in Week 12 for 14 days wear time), written instructions and additional resources (YouTube video) for placing (or replacing) the glucose sensors.* Those in both groups will be *given sample study beverages at baseline (several varieties of still and seltzer water for intervention group or LCSBs matched as possible to those typically consumed in the control group) to encourage adherence. Those in the intervention group will be counseled on avoiding LCSB. Participants and their parent will also be given a brochure on avoiding LCSBs to take home, which will include a list of specific foods and beverages containing LCSBs to avoid during the study. Participants in the control group will be counseled by [name] or a research assistant, and will receive identical counseling on healthy eating as those in the intervention group (in accordance with standard dietary guidance for T1D management), with the exception of information and resources for avoiding LCSB.*

In both groups, text messages will be sent to parents 3X/week with reminders that their child should avoid LCSBs or continue usual intake, per randomization. Adherence will be monitored through collection of spot-urine samples for measurement of sucralose and ace-K concentrations (baseline, week 6, week 12), daily text message beverage logs completed by the parent, and photo-assisted food records with parent assistance in Weeks 0, 6, and 12. During Week 6, participants and their parent will attend a mid-intervention telemedicine booster visit, during which the PI and/or study RA will reinforce the intervention and remind participants to mail back a spot urine sample using materials provided by the study team at baseline (instructions enclosed). Participants will be reminded of the study instructions, including the importance of inserting the DEXCOM G6 sensor (provided by study team) at the beginning of Week 11. Parents will receive a phone reminder to insert the sensor at the end of Week 10 and a second call early in Week 11 to ensure that the sensor has been placed and will be replaced after 7-10 days to allow for 14 days of wear time prior to the follow-up visit. Depending on randomization assignment, guidance to avoid LCSBs or continue usual diet will be reinforced. All participants and their parent will have the opportunity to chat in real-time with the study team about questions or concerns.

At the end of Week 12, participants and their parent will return for follow-up in the CRU. Participants will have their DEXCOM G6™ sensor removed and CGM data downloaded using DEXCOM Clarity™ software. Height and weight will be measured and a urine sample and blood draw performed. Those who had a DXA or BodPod at the baseline visit (n=30) will undergo a second DXA or BodPod, after which these participants and their parent will receive a consultation on the DXA or BodPod results. Those randomized to the intervention will be purposefully sampled and asked to complete a ~20-minute qualitative interview and ~5 minute satisfaction survey, together with their parent, about their study experience and the challenges of LCSB restriction. This will

allow us to collect information from individuals with a range of perspectives and varying degrees of intervention adherence. Sampling will continue until saturation of ideas is reached or until all subjects in the intervention group are invited to be interviewed. Study procedures are detailed below.

Table 1. Timing of Study Procedures			
Time-point	Location	Assessments	Procedures
Interview about COVID-19 impacts on T1D management (separate from rest of trial)	Home	Qualitative interview	Consent, questionnaire, qualitative interview
Screening Visit	Clinic or Home	Eligibility Determination, Enrollment, Questionnaires	Screener, consent, assent, EAT, self-care (SCI), COVID-19 questionnaire, PROMIS questionnaire
Week 0	Home	Diet assessment, glycemic variability	Food record, CGM, beverage log
Baseline Visit	CRU	Glycemic control (HbA1c), lipids, inflammation, visceral adiposity, anthropometrics	Height/weight, spot urine, blood draw, CGM download, DXA or BodPod (subset)
Weeks 1-5	Home	Adherence	Food record, beverage log
Week 6	Home	Diet assessment, adherence, intervention booster	Food record, beverage log, spot urine
Week 7-10	Home	Adherence	Beverage log
Week 11-12	Home	Diet assessment, glycemic variability, adherence	Food record, CGM, beverage log
Follow-up Visit	CRU	Glycemic control (HbA1c), lipids, inflammation, visceral adiposity, anthropometrics, acceptability, feasibility	Height/weight, spot urine, blood draw, SCI, satisfaction survey, qualitative interview, CGM download (for weeks 11 and 12), DXA or BodPod

Laboratory analyses: All blood assays will be run by LabCorps. Urine analyses will be performed by the Clinical Mass Spectrometry Laboratory at the National Institutes of Health. Blood and urine samples will be shipped by certified personnel in the CTSI-CN PCI at Children's National.

Additional blood and urine specimens will be stored in the CTSI-CN PCI at Children's National for up to three years after completion of data collection for future analyses. All samples will be stored deidentified. Depending on the future analyses performed, deidentified samples may be shipped to external commercial or academic laboratories in the future.

